# 2.2. Study Agent/Device/Imaging procedure

# F-FSPG PET/MRI or PET/CT Imaging of Cardiac Sarcoidosis or Inflammation

**Methods:** Here we will evaluate the detection of cardiac sarcoidosis or inflammation using F-FSPG PET/MRI or PET/CT. PET/CT will be used for patients with metal implants who are not eligible for MRI due to safety reasons. We will recruit patients from Division of Cardiology (Sarcoidosis Clinic) at Stanford University. We plan to recruit a total of 50 patients over 4 years who have suspected cardiac sarcoidosis or inflammation, after receiving F FDG PET/CT as standard of care. Potential subjects will undergo preliminary evaluation to ensure eligibility, receive and sign an informed consent and be enrolled in the trial.

PET/MRI scans will be performed with a whole-body PET/MR imaging system capable of simultaneous PET and MR imaging (SIGNA, GE Healthcare, Milwaukee, WI), 45-60 minutes after injection of (+/-20%) 8 mCi of F-FSPG. The system consists of a 3T MR imager that contains a PET detector based on lutetium oxyorthosilicate scintillators coupled to silicon photomultiplier detector (SiPM) technology. PET events will be detected throughout the entire cardiac MRI acquisition in one bed position centered over the heart. A coronal T1-weighted 3D encoded spoiled gradient-echo sequence will be acquired for attenuation correction.

Cardiac MRI sequences will include breath-hold, ECG-triggered balanced cine SSFP for assessment of ventricular size and function by a stack of short axis slices (slice thickness 8 mm, TR 3.0 ms, TE 1.5 ms, flip angle 50°, temporal resolution 35 ms; in-plane resolution 1.7×1.4 mm), and two-dimensional (2D) turbo inversion-recovery magnitude T2-weighted imaging in short axis for assessment of myocardial inflammation and edema (slice thickness 8 mm, TR 2000 ms, TE 44 ms, flip angle 180°, inversion time 180 ms, in-plane resolution 1.3×1.4 mm). Late gadolinium enhanced (LGE) imaging will be performed 15 minutes following administration

of 0.15 mmol/kg bodyweight of MultiHance (Bracco Diagnostics Inc, Monroe Township, NJ) employing a 2D inversion recovery gradient-recalled echo sequence (IR GRE) in short-axis (slice thickness 8 mm, TR 6.5 ms, TE 1.5 ms; flip angle 20°; inversion times 220-360 ms; in-plane resolution 1.8×1.4 mm). Two-, three- and four-chamber LGE planes will also be obtained.

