PET/CT will be performed using Discovery MI PET/CT scanner (GE Healthcare). In brief, PET/CT images will be acquired in 3D mode approximately 45-60 minutes after injection of F FSPG. First, a vertex to mid-thighs scan is done, followed by dedicated imaging of the heart over 1 bed. ToF is standard on the digital PET/CT system. Data driven gating will be acquired according to the vendor's protocol (once commercially available). The PET emission scan is corrected using segmented attenuation data of the CT scan. The PET images are reconstructed both with a standard iterative algorithm (OSEM, two iterative steps, 28 subsets), as well as a regularized reconstruction algorithm (Q.Clear®) provided by GE Healthcare.

**Interpretation of Results:** All images are reformatted into axial, coronal, and sagittal views and viewed with the software available in the Nuclear Medicine and Molecular Imaging Clinic (MIM Vista). PET images will be interpreted by two radiologists in consensus ([name] and [name]). A third reader ([name]) will serve as referee to achieve consensus.

PET image interpretation will begin with identification of areas of myocardial F-FSPG uptake on PET/MRI images using multi-planar reformations and maximum-intensity projections. Myocardial F-FSPG uptake will be globally classified into one of four patterns (none, diffuse, focal, or focal on diffuse) for each participant. Diffuse, focal and focal on diffuse patterns of F-FSPG uptake will be considered to be positive findings indicative of cardiac involvement. Myocardial segments will be evaluated for focal F-FSPG activity using the 17-segment model recommended by the American Heart Association (AHA). The presence or absence of RV free wall F-FSPG activity will also be evaluated. The whole-body PET/MRI or PET/CT acquisition will be evaluated for findings of extra-cardiac sarcoid.

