#### PET/MRI

First, a localizer MRI scan will be performed to define the table positions after correct positioning of the spatial acquisition window. A coronal 2-point Dixon 3-dimensional volumetric interpolated breath-hold T1-weighted MRI sequence will be acquired and used for the generation of attenuation maps and for anatomic allocation of the PET results. Simultaneously with the start of the MRI sequences, the PET acquisition will start at the same table position, thus ensuring optimal temporal and regional correspondence between MRI and PET data. The PET acquisition time will be continuous during the MRI exam, taking delayed acquisition times and radioactive decay into account. The MRI scans will be acquired during breath-hold in the standard cardiac views including 2,3,4 chamber views and stacked axial and short axis views. Some patients may be given an IV (intravenous) gadolinium-based contrast injection as part of the PET/MRI research study to enhance the results of the study. 10 minutes after contrast injection, MRI delayed enhancement images may be obtained in the standard cardiac views. The protocol director or one of the co-investigators will decide the administration of contrast.

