#### PET/CT

First, a vertex to mid-thighs scan is done, followed by dedicated imaging of the heart over 1 bed. ToF is standard on the digital PET/CT system. Data driven gating will be acquired according to the vendor's protocol (once commercially available). The PET emission scan is corrected using segmented attenuation data of the CT scan. The PET images are reconstructed both with a standard iterative algorithm (OSEM, two iterative steps, 28 subsets), as well as a regularized reconstruction algorithm (Q.Clear®) provided by GE Healthcare.

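### Can extra-cardiac sarcoid be read on PET/MRI when the protocol describes only one PET bed over the heart?

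*Protocol*

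**What the plan says.** The reading rule stands at the end of the interpretation text in Protocol section 2.2: "The whole-body PET/MRI or PET/CT acquisition will be evaluated for findings of extra-cardiac sarcoid".

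For PET/CT, the scan it refers to is set out in section 2.2 and again in section 4: "First, a vertex to mid-thighs scan is done, followed by dedicated imaging of the heart over 1 bed".

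For PET/MRI, the Methods text of section 2.2 says "PET events will be detected throughout the entire cardiac MRI acquisition in one bed position centered over the heart". Section 4 (PET/MRI) adds that "a localizer MRI scan will be performed to define the table positions", that "the PET acquisition will start at the same table position" as the MRI sequences, and that "The MRI scans will be acquired during breath-hold in the standard cardiac views". It gives no head-to-thigh range.

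The scanner is not chosen by chance: "PET/CT will be used for patients with metal implants who are not eligible for MRI due to safety reasons". PET/MRI is thus the default and PET/CT the exception.

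**The concern.** Set against the acquisition text, the reading rule seems to ask for something that PET/MRI does not deliver. A single bed centred on the heart cannot show disease in regions outside that field, yet readers are told to look for extra-cardiac disease on a whole-body PET/MRI acquisition. The other use of the term whole-body for PET/MRI, in the Methods text, describes the machine and not the range scanned.

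If no whole-body PET/MRI pass is performed, three things could go wrong:

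- The rule could not be followed outside the cardiac bed for anyone on the default scanner.
- Extra-cardiac findings would not be comparable between scanners, because coverage would follow implant status.
- A region that was never imaged might be recorded as free of disease.

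Scan coverage and reading tasks belong in a protocol, so this cannot simply be assumed to be settled in an analysis plan.

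**Working it through.** The protocol states no figure on this point, so there is nothing to reproduce. The check is a comparison of the texts, followed by a test of whether any planned result depends on the answer.

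**Step 1: what is described for each scanner.**

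| | PET/CT | PET/MRI |
|---|---|---|
| Body-range scan described | Yes, in sections 2.2 and 4 | No |
| Dedicated heart bed described | Yes | Yes |
| Named in the extra-cardiac reading rule | Yes | Yes |

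The empty cell is real: no PET/MRI text gives a body range.

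**Step 2: what the silence can mean.** Three readings fit the text.

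1. *A whole-body PET/MRI pass is done but not described.* The one-bed sentence is confined to PET detected during the cardiac MRI and does not say that no other PET is acquired. The reading rule refers to the acquisition as something that exists. Section 4 has the localizer set table positions in the plural. The PET/CT protocol has the same two-part form, a long scan and then a heart bed.
2. *No such pass is done.* This rests on the missing description, and on section 4 placing PET at the same table position as the cardiac MRI.
3. *The term whole-body is carried over from the name of the scanner.* The rule then asks readers to check whatever was acquired for disease outside the heart. This is less natural, but it can be followed as written.

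The text does not decide among these. It contains no sentence that flatly excludes a whole-body pass.

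**Step 3: what depends on the answer.**

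- Section 1 (Objective) and the primary objective in the synopsis table concern uptake in cardiac disease.
- The rule for a positive scan in section 2.2 rests on the pattern of myocardial uptake, which the cardiac bed supplies on both scanners.
- Section 7 measures feasibility through completed exams and image quality.
- Section 8 states that no statistical analysis is included.
- Section 8.1 plans a larger study if sarcoid is found in more than half the cases. It omits the word cardiac, but the primary objective names cardiac sarcoid as the target.

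No planned quantity uses the extra-cardiac reading.

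**Step 4: what it takes to produce a number.** Take reading 2. Let *f* be the share scanned on PET/CT, assumed to be 10% to 50%. Let *k* be the share of participants with extra-cardiac disease who have some of it inside the cardiac bed, assumed to be 25% to 75%. The protocol gives neither. Participants without described coverage outside the cardiac bed number (1 − *f*)*N*:

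- *N* = 20 (synopsis): 0.50 × 20 = 10 to 0.90 × 20 = 18.
- *N* = 50 (section 2.2: "We plan to recruit a total of 50 patients over 4 years"): 0.50 × 50 = 25 to 0.90 × 50 = 45.

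If findings were also pooled, unimaged regions counted as negative, and extra-cardiac disease equally common in both scanner groups, the pooled rate relative to full coverage would be *f* + (1 − *f*)*k*:

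- lowest: 0.10 + 0.90 × 0.25 = 0.325
- highest: 0.50 + 0.50 × 0.75 = 0.875

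The arithmetic is right but says little about this trial. The range of 33% to 88% reflects the assumed values, and the protocol plans no such rate.

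**The case for a change.** The strongest case for acting is that the protocol describes PET/MRI down to sequence parameters and describes the PET/CT body scan twice. Silence on a whole-body PET/MRI pass is therefore conspicuous, and PET/MRI is the scanner most participants are meant to have. Extra-cardiac disease is also relevant: the example in the background section shows uptake in the pleura and in supraclavicular and thoracic lymph nodes. The remedy would cost a sentence or two.

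Much of this stands. A description is missing, and the PET/MRI texts in sections 2.2 and 4 do not match the reading rule as they are written. An investigator revising the document for another reason could reasonably state whether the pass is acquired.

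What does not stand is the step from a missing description to harm. Nothing in the protocol scores an unimaged region as negative, defines an extra-cardiac endpoint or compares the scanners. Two radiologists read the images, with a third as referee, and they know the field they are looking at. They can be expected to report on the field that was imaged. Allocation of scanner by implant status would matter for a between-scanner comparison or a pooled extra-cardiac rate, but neither is planned.

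**Conclusion.** The observation is correct: a whole-body step is described for PET/CT and not for PET/MRI, while the reading rule names both. It is a gap in description, and it calls for no change to the plan. The myocardial reading, the feasibility measures and the criterion for a larger study are the same whether or not a whole-body PET/MRI pass is done, so the effect on every planned result is zero.

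This rests on two points from the document: the protocol plans no statistical analysis and no extra-cardiac endpoint, and the criterion in section 8.1 is read in line with the primary objective as referring to cardiac sarcoid. It also assumes that readers will not call an unimaged region negative, which is ordinary practice in reading images. If an extra-cardiac rate were later reported across both scanners, the region actually imaged in each participant would have to be stated. That is a matter of reporting and does not alter this plan.

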### 2.3. Clinicaltrials.gov

The study is registered at ClinicalTrials.gov (NCT03103490).

#### 3. PARTICIPANT SELECTION AND ENROLLMENT PROCEDURES

#### 3.1. Inclusion Criteria

- Patient is ≥ 18 years old at the time of the scan
- Patient with known or suspected cardiac sarcoidosis referred for standard of care F FDG PET/CT

- Patient is capable of complying with study procedures
- Patient can remain still for duration of imaging procedure

#### 3.2. Exclusion Criteria

- · Patient is pregnant or nursing
- Metallic implants (contraindicated for MRI; these patients will get PET/CT)
- History of renal insufficiency (only for MRI contrast administration)

#### 4. STUDY PROCEDURE:

Patients will be injected with F-FSPG and undergo the PET/MRI or PET/CT image acquisition after a 45-60 minute delay.

#### PET/MRI

First, a localizer MRI scan will be performed to define the table positions after correct positioning of the spatial acquisition window. A coronal 2-point Dixon 3-dimensional volumetric interpolated breath-hold T1-weighted MRI sequence will be acquired and used for the generation of attenuation maps and for anatomic allocation of the PET results. Simultaneously with the start of the MRI sequences, the PET acquisition will start at the same table position, thus ensuring optimal temporal and regional correspondence between MRI and PET data. The PET acquisition time will be continuous during the MRI exam, taking delayed acquisition times and radioactive decay into account. The MRI scans will be acquired during breath-hold in the standard cardiac views including 2,3,4 chamber views and stacked axial and short axis views. Some patients may be given an IV (intravenous) gadolinium-based contrast injection as part of the PET/MRI research study to enhance the results of the study. 10 minutes after contrast injection, MRI delayed enhancement images may be obtained in the standard cardiac views. The protocol director or one of the co-investigators will decide the administration of contrast.

#### PET/CT

First, a vertex to mid-thighs scan is done, followed by dedicated imaging of the heart over 1 bed. ToF is standard on the digital PET/CT system. Data driven gating will be acquired according to the vendor's protocol (once commercially available). The PET emission scan is corrected using segmented attenuation data of the CT scan. The PET images are reconstructed both with a standard iterative algorithm (OSEM, two iterative steps, 28 subsets), as well as a regularized reconstruction algorithm (Q.Clear®) provided by GE Healthcare.

#### 5. ADVERSE EVENTS AND REPORTING PROCEDURES.

The administration of the radioactive substance will feel like a slight pinprick when given by IV injection. Patients who are claustrophobic may feel some anxiety while positioned in the scanner. Also, some patients find it uncomfortable to hold one position for more than a few minutes. The subjects will not feel anything related to the radioactivity of the substance in their body. Because the radioactivity is very short-lived, the radiation exposure is low. The substance amount is so small that it does not affect the normal processes of the body.

This research study involves exposure to radiation from one F-FSPG PET/MRI scan. The effective dose from one typical administration of F-FSPG is 4.5 mSv, approximately equal to 10% of the limit that radiation workers (for example, a hospital x-ray technician) are allowed to receive in one year. This radiation exposure is for research purposes only.

In case you cannot undergo MRI due to metal implants, PET/CT will be done. CT in PET/CT will add 5 mSv for a total of 9.5 mSv, approximately equal to 20% of the limit that radiation workers (for example, a hospital x-ray technician) are allowed to receive in one year.

Adverse events will be graded according to CTCAE v5.0. Both Serious and Non-Serious Adverse Events will be clearly noted in source documentation and listed on study specific Case Report Forms (CRFs). The Protocol Director (PD) or designee will assess each Adverse Event (AE) to determine whether it is unexpected according to the Informed Consent, Protocol Document, or Investigator's Brochures, and related to the investigation. All Serious Adverse Events (SAEs) will be tracked until resolution and 30 days after the last dose of the study treatment.

#### 6. REGULATORY CONSIDERATIONS

### 6.1. Data and Safety Monitoring Plan

The principal investigator will be responsible for monitoring the safety of subjects who have enrolled in the study.

# 6.2. Confidentiality

All data including data forms, PET/MRI reports, and clinical information will be stored in a locked, secure location within the Division of Nuclear Medicine and Molecular Imaging. Data will only be accessed by members of the research team assigned to data collection or analysis. No information derived from this study will be provided to the subject's personal physician, a government agency, or any other person or group.

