For cardiac MRI analysis, left and right ventricular (LV and RV) endocardial borders will be manually contoured on short-axis SSFP images to assess for end-diastolic and end-systolic volumes, and ejection fraction (EF). LV epicardial borders will also be manually contoured to assess LV mass. Presence of T2-hyperintensity and LGE will be qualitatively assessed by visual inspection of all available images and will be graded as present or absent using the AHA 17-segment model. The pattern of LGE will be classified as either CAD type or non-CAD type as described previously [17]. The presence or absence of RV free wall LGE was also evaluated.

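### Section 6.2, taken literally, bars giving study information to physicians, regulators or the IRB, and the protocol text shown makes no exception for safety reports or urgent findings

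*Protocol*

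**What the plan says.** Section 6.2 (Confidentiality) covers data forms, PET/MRI reports and clinical information. After a storage rule it states: "Data will only be accessed by members of the research team assigned to data collection or analysis". It then closes with: "No information derived from this study will be provided to the subject's personal physician, a government agency, or any other person or group". Neither sentence carries an exception or is limited to identifiable data.

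Section 5 deals with adverse events and, by its title, with reporting procedures. Events are graded, noted in source documents and listed on case report forms. The protocol director or a designee assesses each one to "determine whether it is unexpected according to the Informed Consent, Protocol Document, or Investigator's Brochures, and related to the investigation". For serious events: "All Serious Adverse Events (SAEs) will be tracked until resolution and 30 days after the last dose of the study treatment". No outside recipient is named.

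Section 6.1 (Data and Safety Monitoring Plan) says: "The principal investigator will be responsible for monitoring the safety of subjects who have enrolled in the study". It adds no reporting route.

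Three other places show what information the study can generate:

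- Section 4, PET/MRI: "Some patients may be given an IV (intravenous) gadolinium-based contrast injection as part of the PET/MRI research study".
- Section 3.2 restricts that contrast: "History of renal insufficiency (only for MRI contrast administration".
- Section 2.2, on the cardiac MRI analysis: "Presence of T2-hyperintensity and LGE will be qualitatively assessed by visual inspection of all available images". The same section has the whole-body acquisition read for sarcoid outside the heart.

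**The concern.** A confidentiality clause normally protects identifiable records from uses outside the study. This one is broader: it covers any information derived from the study and any recipient, and it expressly names the personal physician and government agencies. Both may need a safety notice.

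The participants have known or suspected cardiac sarcoidosis and come from a cardiology clinic. They receive an investigational tracer, and some also receive gadolinium for research purposes. A contrast reaction, or an urgent finding on the MRI or CT, could matter for their care within hours or days. A coordinator who follows Section 6.2 to the letter would withhold it from the physician responsible for the patient, and would also withhold a safety report from the IRB or a regulator. What is at stake is patient safety and clear instructions to staff.

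**Working it through.** No arithmetic applies, because the point concerns wording. The check sets the relevant sections side by side and asks what a literal reader may do.

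1. **Scope of the bar.** Section 6.2 reaches information derived from the study and opens by listing data forms, PET/MRI reports and clinical information. Adverse event forms and scan reports fall within that list on an ordinary reading.

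2. **Recipients barred.** The personal physician and government agencies are named. A treating physician is not named, and may be a different person from the personal physician, since patients are recruited from the Sarcoidosis Clinic. A treating physician is caught only by the closing catch-all. So is the IRB, although the eligibility checklist in the Appendix refers to IRB approval of the study.

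3. **Search for an exception.** Sections 1 to 8, the Appendix checklist and the references were read for any carve-out covering safety reports, regulators, the IRB, treating physicians, or urgent or incidental findings. None appears in the text shown.

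4. **Comparison with Section 5.** Grading, recording, assessing and tracking can all be done within the team, so none of these steps breaches Section 6.2. But judging whether an event is unexpected and related usually serves to decide whether it must be reported onward, and the section's title mentions reporting. The tension is therefore an inference from the title and the assessment step; no written duty to report to an outside party is contradicted.

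5. **Information affected.**

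| Information | Source in the protocol | Under Section 6.2 as worded |
|---|---|---|
| Adverse event, including a reaction to research gadolinium | Sections 3.2, 4 and 5 | Not to be given to the personal or treating physician, the IRB or a regulator |
| Urgent finding on cardiac MRI | Section 2.2 | Not to be given to the personal or treating physician |
| Urgent finding on CT or whole-body images | Sections 2.2 and 4 | Not to be given to the personal or treating physician |
| Routine 18F-FSPG read | Section 2.2 | Not to be given; can be a legitimate choice |

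6. **Size.** The sentence applies to every participant: 20 according to the synopsis, 50 according to Section 2.2. That describes scope, not harm. The documents give no rate of reportable events or urgent findings, so no frequency can be derived.

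**The case against.** The best defence is that the sentence closes a short section on confidentiality, straight after storage and access rules, and is plainly about protecting records. Adverse events have their own section, and a specific section would normally govern over a general one. The study is registered (Section 2.3) and refers to IRB approval, so a total bar cannot have been intended. The consent pages are not shown and may hold the usual terms on regulator access and incidental findings. Withholding research reads of an investigational tracer can also be deliberate. Whether a contrast reaction counts as information derived from the study, rather than as a clinical event in the source record, is open to argument.

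Much of this stands as an account of intent, and it limits the weight of the point. It does not cure the text. Section 5 sets out no outside reporting step that could take precedence over Section 6.2, and a consent form with exceptions would leave the two documents in disagreement.

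A reader might go further in three ways, none of which the documents support:

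- **That Section 6.2 contradicts a written reporting duty.** Section 5 names no outside recipient, so the conflict is inferred.
- **That the clause expressly names the treating physician.** It names the personal physician; others fall under the catch-all.
- **That it is the only disclosure rule for the study.** With the consent pages not shown, this cannot be confirmed. One can say only that the protocol text shown contains no exception.

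Nor do the documents show that staff would in fact withhold safety information.

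**Conclusion.** The point holds as a correction to wording. Read literally, Section 6.2 bars safety reports to the IRB or regulators, and notice to the personal or treating physician of adverse events or of urgent findings on MRI, CT or whole-body images. It sits badly with Section 5 without contradicting a stated duty there. This is a rule that is present and unsafe if followed, rather than a detail left for another document.

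Severity is low. The intended meaning is probably narrower, oversight exists, and no endpoint, estimate or sample size is affected. The conclusion assumes that adverse events and scan findings count as information derived from the study, which is the ordinary reading of the section's own list. It does not depend on what the consent form says.

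**What to change.** In Section 6.2, limit the bar to identifiable data for purposes outside the study, and add two exceptions:

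1. safety reports to, and record access by, the IRB and regulators as required;
2. notice to the subject's personal or treating physician of adverse events, including contrast reactions, and of urgent, clinically important findings noted on the images.

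If routine investigational 18F-FSPG reads are not to be returned, say so as a deliberate choice.

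The cost is two or three sentences, plus matching consent text if the consent form does not already say this. Design, procedures and sample size stay as they are.
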